13.1. Definitions

The following definitions will apply to the reporting of adverse events:

1. **Serious Adverse Event:** Any adverse experience occurring at any dose that is fatal or life threatening; requires in-patient hospitalization or prolongation of an existing hospitalization; is a persistent significant disability/incapacity; is a congenital anomaly or birth defect; or is an important medical event that may not result in death, be life-threatening, or require hospitalization but, based upon appropriate medical judgment, may jeopardize the subject and may require medical or surgical intervention to prevent one of the outcomes listed above.
2. **Unexpected Adverse Event:** Any adverse experience that is not identified in nature, severity, or frequency in the Investigator's Brochure for NTZ or the respective prescribing information for TDF, TAF or ETV.
3. **Severity of adverse events** will be assessed by the Investigator using the Toxicity Grading Scale Tables provided in [Section 23.3](#) (derived and adapted from "Division of AIDS Table for Grading the Severity of Adult and Pediatric Adverse Events," Version 2.1, Publish Date: July 2017)
4. **Causality (relationship to treatment)** will be assessed as follows:

The Investigator will assess causal relationship between Investigational Product and each adverse event and answer "yes" or "no" to the question, "Do you consider that there is a reasonable possibility that the event may have been caused by the Investigational Product?" Under double-blind treatment conditions, it should be assumed that all subjects are taking the test drug.

13.2. Clinical Adverse Events

At the time of each return visit, the subject will be questioned regarding the occurrence and nature of any adverse events. All events must be recorded in the subjects' medical records and in the EDC system. Any subject affected will be examined by the Investigator as deemed necessary to ascertain the course of the event and any residual effects.

All moderate and severe adverse events will be reviewed by the Principal Investigator who will determine using his/her best clinical judgment whether they warrant the subject to be discontinued from the study. The Sponsor will be notified immediately if a subject is discontinued from the study. For all adverse events that require the subject to be discontinued from the study, relevant clinical assessments and laboratory tests will be repeated as clinically indicated until final resolution or stabilization of the event(s).

All subjects will be instructed to contact the Investigator, Investigator's assistants, or clinical personnel should the subject have any serious adverse experiences. Serious adverse events,

including death regardless of the cause, must be reported to the Sponsor immediately (within 24 hours of the initial report).

A serious event requiring immediate notification by telephone is an event that:

- results in death
- is life threatening
- requires inpatient hospitalization or prolongation of an existing hospitalization
- is a persistent or significant disability/incapacity
- is a congenital anomaly/birth defect
- an important medical event that may not result in death, be life-threatening, or require hospitalization but, based upon appropriate medical judgment, may jeopardize the subject and may require medical or surgical intervention to prevent one of the outcomes listed above.

An overdose is defined as any intentional or unintentional consumption of the drug by any route that exceeds the highest dose stated in the Investigator's Brochure, approved product labeling (for TDF, TAF or ETV) or in an investigational protocol, whichever dose is larger. Overdoses without an associated adverse event should be recorded, but not reported as an adverse event.

13.3. Reporting Requirement

The Principal Investigator is required to notify The Romark Institute for Medical Research (Sponsor) within 24 hours of learning of any unexpected, fatal, or life-threatening experience and all unusual, alarming, or serious reactions to medication regardless of any opinions as to the cause/effect relationship. All serious adverse events will also be reported to the IRB. Adverse events should be reported to:

The Romark Institute for Medical Research

Medical Affairs

[REDACTED]

13.4. Medication Modification/Withdrawal Due to Adverse Event

If a severe adverse reaction or laboratory abnormality develops during combination therapy, the dose should be modified or discontinued, at the discretion of the Investigator and in accordance with the approved product labeling for TDF, TAF or ETV, until the adverse reaction abates. If intolerance persists after the dose has been adjusted, the study medication should be discontinued.

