9.6. Study Medication Discontinuation and Withdrawal Criteria

Treatment with the investigational medication (NTZ/placebo) will be discontinued for individual subjects for the following reasons:

1. Subject withdraws consent.
2. A subject must discontinue study medication for the following medical or administrative reasons [reasons for discontinuing must be recorded in the case report form (CRF)]:
 - Violation of eligibility criteria.
 - Material deviation from the treatment plan specified in the protocol.
 - Progression of the disease which in the opinion of the investigator precludes further participation.
 - Women who become pregnant.
3. An adverse event deemed sufficiently severe to require study discontinuation. These include:
 - Grade 2 or higher rash at least possibly related to study drug.
 - Grade 3 or 4 acute systemic allergic reaction.
 - Grade 2 serum creatinine considered at least possibly related to the study drug by the investigator, or Grade 3 or 4 proteinuria on urinalysis, confirmed by retesting.
 - Grade 2 vomiting that persists despite anti-emetics, or Grade 3 or higher vomiting.
 - Grade 3 or higher diarrhea at least possibly related to study drug.

- Treatment-emergent elevation of ALT greater than 2x baseline, in combination with either bilirubin greater than 2x the upper limit of normal (ULN) or INR greater than 1.5x ULN or serum albumin less than the lower limit of normal (LLN), confirmed by retesting.
- Any Grade 4 AE or confirmed abnormality (except for AST/ALT elevations) considered at least possibly related to the study drug.
- Clinical signs of hepatic decompensation.
- QTcF prolongation (QTcF greater than 500 msec, or increase from baseline greater than 60 msec) at any time point, confirmed by repeat ECG.

4. Subject is:

- HBsAg positive with no decline in qHBsAg from Baseline at Week 12.
- HBsAg positive with less than a $0.5 \log_{10}$ decline in qHBsAg from Baseline at Week 24.
- HBsAg positive with less than a $1 \log_{10}$ decline in qHBsAg from Baseline at Week 48.
- HBsAg positive with less than a $2 \log_{10}$ decline in qHBsAg from Baseline at Week 72.
- HBsAg positive at Week 96.

5. HBsAg loss with HBV DNA suppression maintained on treatment for 24 weeks (consolidating therapy).

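### Section 13.4 lets the investigator modify the dose after a severe reaction, including events for which Section 9.6 requires discontinuation, without saying which section governs or which product is meant

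*Combined protocol and SAP*

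**What the plan says.** Section 9.6 opens with a mandatory statement: "Treatment with the investigational medication (NTZ/placebo) will be discontinued for individual subjects for the following reasons". Item 3 of its list is headed "An adverse event deemed sufficiently severe to require study discontinuation" and gives named events. Among them are "Grade 3 or higher diarrhea at least possibly related to study drug" and "Grade 3 or 4 acute systemic allergic reaction", as well as vomiting of Grade 3 or above, and rash of Grade 2 or above that is at least possibly related. A notice at the end of the section reserves discontinuation of TDF, TAF or ETV for subjects who have kept HBsAg loss with HBV DNA suppression through 24 weeks of consolidating therapy. All other subjects stay on their NrtI.

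Section 13.4 has a different rule. Its trigger is broad: "If a severe adverse reaction or laboratory abnormality develops during combination therapy". Its action is that "the dose should be modified or discontinued, at the discretion of the Investigator". It adds that this should follow the approved labeling for TDF, TAF or ETV and should last until the reaction subsides. It ends: "If intolerance persists after the dose has been adjusted, the study medication should be discontinued".

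Section 13.2 covers moderate and severe events. It says that the Principal Investigator "will determine using his/her best clinical judgment whether they warrant the subject to be discontinued from the study".

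The grading table in Section 23.3 labels Grade 3 as severe.

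**The concern.** An event can meet both triggers. One section then takes the subject off NTZ/placebo, while the other allows the subject to stay on at a changed dose, or to stop only for a time. No order of precedence is stated. The rule concerned protects subjects, and Section 16 says that no independent data monitoring committee will review the data.

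The product is also unclear. The labeling reference in Section 13.4 points to the NrtI, but its last sentence stops the study medication. Section 12.2 describes the packaging of all study medication and covers only NTZ and placebo tablets.

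There is a secondary stake for the analysis. If Section 13.4 does permit changes to blinded NTZ/placebo, a dose-range-finding trial with 12 subjects per arm could contain subjects who are no longer on their randomized dose, and the plan does not say how they would be handled.

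**Working it through.** The plan gives no figure on this point, and its sample-size calculation does not depend on it. The check is a comparison of texts, followed by conditional tablet arithmetic.

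**Step 1: do the triggers overlap?** Item 3 of Section 9.6 has nine entries. Four of them reach Grade 3, which is severe on the trial's scale, and also fit the Section 13.4 trigger when regarded as reactions:

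| Event | Section 9.6 | Section 13.4 |
|---|---|---|
| Related diarrhea, Grade 3 or above | Discontinue | Modify or discontinue until it subsides; stop if intolerance persists |
| Systemic allergic reaction, Grade 3 or 4 | Discontinue | Same |
| Vomiting, Grade 3 or above | Discontinue | Same |
| Related rash, Grade 3 or above (9.6 starts at Grade 2) | Discontinue | Same |

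The overlap has limits. The Grade 2 entries in Section 9.6 (rash, persistent vomiting, creatinine) are moderate on the scale and fall outside Section 13.4 if *severe* qualifies both nouns in its trigger. The vomiting and allergic-reaction entries carry no causality condition, so they overlap only where the event is regarded as a reaction.

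**Step 2: does Section 13.4 yield to Section 9.6?** It contains no exception for listed events and no cross-reference, and no other section sets an order. The revision history (Amendment 2, Change 7) records that discontinuation events were added to Section 9.6 on FDA's recommendation, and it logs no matching change to Section 13.4. That may explain how the mismatch arose. The conflict itself lies in the current text.

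**Step 3: which product is *the dose*?**
- If NTZ/placebo: the option to modify conflicts with the mandatory discontinuation in Section 9.6 for the events in Step 1.
- If the NrtI: the option to discontinue conflicts with the notice closing Section 9.6, and with Section 6, which keeps all subjects on their NrtI throughout.

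Neither reading removes the inconsistency.

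**Step 4: conditional arithmetic.** This applies only if blinded tablets may be reduced. The inputs are the tablet contents in Section 6 (300 mg per NTZ tablet) and the six bottles in Section 12.2, with one tablet taken from each per day. Which bottle holds placebo in Groups 2 and 3 is not stated, so ranges are shown. Daily NTZ = 300 mg × number of NTZ tablets.

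| Group | NTZ tablets (morning + evening) | Full daily dose | One tablet removed at each intake |
|---|---|---|---|
| 1 | 0 + 0 | 0 mg | 0 mg |
| 2 | 2 + 0 | 600 mg | 600 or 300 mg |
| 3 | 2 + 2 | 1200 mg | 1200, 900 or 600 mg |
| 4 | 3 + 3 | 1800 mg | 1200 mg |

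One blinded instruction would thus remove 0 mg, 0 to 300 mg, 0 to 600 mg or 600 mg of NTZ per day, depending on the arm. A Group 4 subject would end on Group 3's full daily total. Two of six tablets is 2/6 = 33%, above the 20% missed-dose threshold for non-compliance in Section 12.4; one of six is 16.7%, below it. The plan does not say whether a reduction directed by the investigator counts as missed doses.

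**The case against.** The strongest reply is that the two sections can be read together. Section 13.4 includes discontinuation as an option, covers many severe events that Section 9.6 does not list individually, and ties discretion to NrtI labeling. An investigator who stops treatment for related Grade 3 diarrhea satisfies both sections, and a reader may treat the specific list as prevailing over the general rule. It is true that both can be obeyed at once. But the protocol never says that the list prevails, and Section 13.4 on its face permits a course that Section 9.6 does not.

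Three stronger readings are tempting, and the documents do not support them.

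- *Investigators would act in opposite ways on the same event.* The synopsis names one center, and Section 13.2 sends all moderate and severe events to the Principal Investigator. Room for divergence is limited.
- *Section 13.2 is a third contradictory rule.* It concerns leaving the study, whereas Section 9.6 opens with stopping the investigational medication, and Section 13.2 itself recognizes events that require discontinuation. The item 3 heading in Section 9.6 blurs the distinction by speaking of study discontinuation, so the wording needs aligning, but the clash is weaker.
- *Blinded tablet reductions will distort the dose comparison.* No section describes dropping a tablet or bottle, and the labels direct one tablet from every bottle. The number of subjects affected is unknown. The primary analysis is by randomized group, and trough tizoxanide is sampled at each on-treatment visit, so altered exposure could be observed. The arithmetic in Step 4 shows what would follow if reductions were allowed; it does not show that they are.

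**Conclusion.** The concern holds as a conflict between stated safety rules. Using the modification option in Section 13.4 would keep on treatment a subject whom Section 9.6 takes off. It reaches at least four of the nine entries in item 3, at Grade 3 and above. This rests on taking *severe* in Section 13.4 to include Grade 3, as the trial's own table does. The product ambiguity adds to the problem rather than resolving it, because the NrtI reading meets a separate conflict within Section 9.6. The effect of a tablet reduction across arms is secondary and depends on *the dose* meaning NTZ/placebo. No stated figure is wrong, and no effect on power or on the primary comparison is shown. The point should be fixed because it bears on subject safety and costs almost nothing. Which clinical rule should apply is not for this review to decide.

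**What to change.** Reconcile Section 13.4 with item 3 and the closing notice of Section 9.6, so that each listed event has one stated action, and name the section that governs those events. State in Section 13.4 whether the dose means NTZ/placebo, the NrtI or both. Align Section 13.2 and the item 3 heading on whether they mean stopping study medication or leaving the study. State whether blinded study medication may be reduced. If it may, say how the reduction is recorded, whether it counts toward the 20% missed-dose threshold in Section 12.4, and how such subjects are treated in the per-protocol population. The sponsor sets the clinical content.

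The cost is protocol wording, with the IRB review that Section 18.3 requires for a non-administrative amendment. Reconciling the sections changes neither the sample size nor the visit schedule.

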13.5. Medication Errors

A medication error is defined as any preventable event related to dosing instructions, product labeling, or packaging that causes or leads to inappropriate medication use or subject harm while the medication is in the control of the investigative site or subject. Medication errors which result in adverse events should be recorded and reported as adverse events. All other medication errors should be reported to the study Sponsor through the Medical Affairs department within 7 days of identification by the site.

14. DISCONTINUATION

The study may be discontinued under the following circumstances:

1. The Sponsor reserves the right to discontinue the study at any time.
2. Adverse event listings will be produced for safety monitoring at least once every two weeks during recruitment. The data will be tested to determine if there are greater than 20% of the subjects who have had at least Grade 3 adverse events considered by the Investigator to be related to the study drug (defined by the Toxicity Grading Scale Tables provided in [Section 23.3](#)).

If greater than 20% of the subjects have at least one Grade 3 or Grade 4 adverse event considered to be related to the study drug by the study Medical Monitor, then the study must be stopped and the Institutional Review Boards, local regulatory authorities and FDA's Division of Antiviral Drug Products will be notified. All safety and activity data will be submitted to the FDA in a timely manner.

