13. ADVERSE EVENTS

The term “adverse event” is defined for purposes of this study as any unwanted physical, psychological or behavioral change experienced by a subject during the course of the study and after taking the first dose of study medication regardless of its severity or relation to the study. Adverse events may include symptoms, signs, unexpected worsening of pre-existing conditions, clinically significant changes in laboratory values, diseases and syndromes, and significant and unexpected failures of pharmacological action of other medications. Symptoms of CHB will not be reported as adverse events.

Adverse events will be recorded on the appropriate EDC forms throughout the study, and the severity of each adverse event will be graded on a four-point scale: mild, moderate, severe, or life-threatening (See [Section 23.3](#)). The duration of the adverse event and relationship to the study drug will also be recorded. All adverse events must be followed until their resolution or stabilization even beyond the planned study period.

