23.3. Appendix III: Toxicity Grading for Adult Adverse Events

See “Division of AIDS Table for Grading the Severity of Adult and Pediatric Adverse Events; Version 2.1, Publish Date: July 2017” (Table 5).

General Instructions

Estimating Severity Grade: If the need arises to grade a clinical adverse event that is not identified in this table, use the category “Estimating Severity Grade” located at the top of Table 5. In addition, all deaths related to an AE are to be classified as Grade 5.

Determining Severity of Grade: If the severity of an adverse event could fall under either one of two grades (e.g., the severity of an adverse event could be either Grade 2 or Grade 3), select the higher of the two grades for the adverse event.

Table 5: Division of AIDS Table for Grading the Severity of Adult and Pediatric Adverse Events; Version 2.1, Publish Date: July 2017

PARAMETER	GRADE 1 MILD	GRADE 2 MODERATE	GRADE 3 SEVERE	GRADE 4 POTENTIALLY LIFE-THREATENING
ESTIMATING SEVERITY GRADE				
Clinical adverse event NOT identified elsewhere in this grading table	Mild symptoms causing no or minimal interference with usual social & functional activities with intervention not indicated	Moderate symptoms causing greater than minimal interference with usual social & functional activities with intervention indicated	Severe symptoms causing inability to perform usual social & functional activities with intervention or hospitalization indicated	Potentially life-threatening symptoms causing inability to perform basic self-care functions with intervention indicated to prevent permanent impairment, persistent disability, or death
CLINICAL- CARDIOVASCULAR				
Arrhythmia (by ECG or physical examination) Specify type, if applicable	No symptoms AND No intervention indicated	No symptoms AND Non-urgent intervention indicated	Non-life-threatening symptoms AND Non-urgent intervention indicated	Life-threatening arrhythmia OR Urgent intervention indicated
Blood Pressure Abnormalities Hypertension (with the lowest reading taken after repeat testing during a visit) ≥ 18 years of age	140 to < 160 mmHg systolic OR 90 to < 100 mmHg diastolic	≥ 160 to < 180 mmHg systolic OR ≥ 100 to < 110 mmHg diastolic	≥ 180 mmHg systolic OR ≥ 110 mmHg diastolic	Life-threatening consequences in a participant not previously diagnosed with hypertension (e.g., malignant hypertension) OR Hospitalization indicated

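### Section 14's mandatory safety stop leaves adverse-event-related deaths out of its count, and the test that feeds it is scheduled only during recruitment

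*Combined protocol and SAP*

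**What the plan says.** Section 14 sets out the rule in steps.

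- Schedule: "Adverse event listings will be produced for safety monitoring at least once every two weeks during recruitment".
- Test: the data are checked for more than 20% of subjects with "at least Grade 3 adverse events considered by the Investigator to be related to the study drug".
- Stop: "If greater than 20% of the subjects have at least one Grade 3 or Grade 4 adverse event considered to be related". The sentence goes on: "considered to be related to the study drug by the study Medical Monitor, then the study must be stopped".

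The same section keeps a general discretion: "The Sponsor reserves the right to discontinue the study at any time".

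On grading, Section 13 has adverse events "graded on a four-point scale: mild, moderate, severe, or life-threatening", which gives no grade to death. Appendix III (Section 23.3) adds that "all deaths related to an AE are to be classified as Grade 5". On causality, Section 13.1 says: "The Investigator will assess causal relationship between Investigational Product and each adverse event".

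On duration, Sections 6 and 9.6 give every subject a planned 12 weeks of study drug. Responders continue under decline criteria that run to Week 96, and a subject who loses HBsAg has 24 weeks of consolidation. Sections 6 and 11.4.1 plan a safety and primary efficacy analysis, unblinded to the Sponsor and Medical Monitor, once all subjects have completed Week 12. Section 16 states that there is no independent data monitoring committee.

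**The concern.** The test sentence and the stop sentence do not count the same events, and only the stop sentence has a consequence. The events they treat differently are deaths, the most serious outcome the rule could meet.

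The stop sentence has no end date, but the only schedule for producing the data it needs ends with recruitment. Exposure does not end then. The last subjects enrolled have nearly all of their first 12 weeks ahead of them, and the long exposures that the extension is meant to allow come later still.

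With no independent committee to interpret the rule, the Sponsor and Medical Monitor have to apply it as written. Read that way, it could fail to fire when a related death should have tipped it, or fire later than it should.

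**Working it through.** The plan gives no operating characteristics for the 20% rule, so there is no stated figure to reproduce.

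**Deaths**

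Inputs: 48 subjects (Section 6), the 20% threshold and two grade ranges (Section 14), and Grade 5 for related deaths (Appendix III).

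Let c be the number of subjects with at least one related Grade 3 or 4 event, d the number of related deaths without such an event already counted, and n the denominator.

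- Test wording: (c + d)/n > 0.20.
- Stop wording: c/n > 0.20.
- The two disagree when c ≤ 0.20n < c + d.

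At n = 48, 0.20 × 48 = 9.6, so 10 subjects are needed. With d = 1 the wordings disagree only at c = 9: 10/48 = 20.8% against 9/48 = 18.75%. With d = 2 they disagree at c = 8 or 9.

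If n means subjects dosed to date, the gap can also open early. One related death among the first 4 dosed, with nothing else counted, is 1/4 = 25% on the test wording and 0/4 on the stop wording.

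**Schedule**

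Inputs: 48 subjects, 12 weeks of planned dosing, and a screening window of August 2019 through April 2020 (Section 1). Accrual is assumed uniform over T weeks, with T = 36 as the working value.

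- Subjects still within 12 weeks of enrolment when recruitment closes: 48 × 12/T. This is 16 at T = 36, 19.2 at T = 30 and 14.4 at T = 40.
- Share of first-12-week dosing still to come: at T = 36, 16 subjects with 6 weeks left on average is 16 × 6 = 96 of 48 × 12 = 576 subject-weeks, or 16.7%.
- Extension phase: the first subject enrolled is at about Week 36 when recruitment closes (T = 36). No dosing after that point, through Week 96 or beyond, falls within the period when listings are required.

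**Effect of the Week 12 safety analysis**

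After recruitment closes the denominator is fixed and the count of affected subjects can only rise. A crossing in the next 12 weeks is therefore still visible when the last subject reaches Week 12. The analysis planned for that moment would show it, up to 12 weeks after it occurred.

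Simulation agrees. The assumptions were uniform 36-week accrual, events spread over 12 weeks, two-weekly looks, and the rule applying from 12 enrolled.

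| True related rate, all arms | Looks end with recruitment | Two-weekly looks for 12 more weeks | Single look at last subject's Week 12 |
|---|---|---|---|
| 25% | about 70% | about 83% | about 83% |
| 30% | about 88% | about 96% | about 96% |

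The last two columns match. For the first 12 weeks, continued looks buy earlier detection and no additional detection, provided the rule is applied at the Week 12 analysis. Section 14 does not say that it is.

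**The case against.** The case for leaving the rule alone has real force, and several stronger readings fail.

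- **Deaths are unmonitored.** They are not. Section 13.2 requires serious events, including any death, to reach the Sponsor within 24 hours, and the Sponsor may stop the trial at any time. A fatal case may also already have a counted Grade 3 or 4 event. The omission is in the wording of the rule, and at 48 subjects with one uncounted death it changes the result at only one count.
- **The stop lapses when recruitment ends.** The stop sentence has no time limit; only the listings are tied to recruitment. Adverse events are still reviewed at every visit, and individual stopping criteria (Section 9.6) still apply.
- **Ending the listings loses detections.** The rises from 70% to 83% and from 88% to 96% suggest this, but they treat the Week 12 safety analysis as absent. What remains is a delay of up to 12 weeks and an unscheduled extension phase.
- **Nobody is named to decide, and there is no denominator.** The stop sentence names the Medical Monitor, and an Investigator screen followed by a Medical Monitor decision is the ordinary reading. Section 11.4.2 bases safety assessment on randomized subjects who received study medication. Only the words to date are missing.
- **The rule needs a minimum number of subjects.** Without one, a single event among the first four can force a stop on the dosed-to-date reading. A simulated false-stop chance of about 15.7% needs an assumed 5% related rate with every event immediate; spread over 12 weeks it is about 2.4%. A minimum of 12 also has a price. With assumed rates of 50% in one arm and 2% elsewhere, it lowers automatic stopping from about 55% to 34% (immediate events) or from about 15% to 9% (spread). A sensitive early rule is defensible here, so this is a trade-off and not a defect.

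What survives is the grade mismatch and the gap in the schedule.

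**Conclusion.** Two defects hold, both minor. The grade mismatch follows from the text alone and needs no assumption about event rates. The schedule gap also follows from the text. Its size, about 16 of 48 subjects (14 to 19 for accrual of 40 to 30 weeks), rests on assumed uniform accrual. The consequence in the first 12 weeks is delay; in the extension it is the lack of any planned test.

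The documents do not show that subjects are left unprotected, and efficacy inference is not affected. The changes are still worth making, because this is the plan's only mandatory study-level stop and the cost is very small.

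**What to change.** Amend Section 14 as follows.

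1. Use Grade 3 or higher, including Grade 5, in both the test and the stop sentence.
2. Continue the listings and the 20% test while any subject is on study drug: for example, every two weeks until the last subject's Week 12, then at a stated interval through the extension.
3. For clarity, state that the Investigator's assessment is the screen and the Medical Monitor's count decides, and that the denominator is subjects dosed to date.

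The cost is a short amendment and a little more listing work after recruitment. A minimum number before the automatic stop applies, or a masked by-arm table prepared by the holder of the randomization list, may be considered as options. The first lowers early sensitivity, and the second would have the list holder handle event data by arm. Neither is needed to correct the two defects.
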